#### 11.2.1.3 Accuracy by Organ

The MMRM logistic regression model (1) will be used for each organ. The analyses will be the same as those for accuracy by site. However, as shown in Table 1, sample sizes are small for some organs, e.g., hernial/peritoneal, gallbladder, appendix, etc. Should convergence not be reachable for model (1), cross tabulation of the observed, unmodeled major discordance rates for the two modalities will be presented. In all cases, the observed, unmodeled major discordance rates for the two modalities and the WSI – Glass difference will be presented by organ in a tabular format for all organs.

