#### **11.1.2 Primary Analysis of Non-inferiority of WSI Relative to Glass**

##### Primary Analysis Model

The primary analysis of the adjudicated comparison of each modality to the GT diagnosis will be performed using a repeated measures logistic regression model. In this model, the dependent variable is major discordance status, yes versus no. Modality (Glass or WSI), will be included in the model as fixed effect; and, site, reader, and case will be included as random effects. The AAP will be used for the primary analysis; however, any reading classified as “deferred” or as missing data will be excluded. The mixed model repeated measure (MMRM) logistic regression model can be written as:

$$\text{Ln} \left[ \frac{P(Y_{ilfh} = 1)}{1 - P(Y_{ilfh} = 1)} \right] = \mu + \alpha_i + s_l + r_{f(l)} + \beta_{h(l*j)} + \varepsilon_{ilfh} \quad (1)$$

where  $P(Y_{ilfh} = 1)$  is the probability that the diagnosis is discordant with GT and  $Y_{ilfh}$  is the dichotomous outcome for case  $h$  ( $h = 1, 2, \dots, 250$ ), by reader  $f$  ( $f = 1, 2, 3, 4$ ), within site  $l$  ( $l = 1, 2, 3, 4$ ) using modality  $i$  ( $i = 1, 2$ ).

$\mu$  is the overall mean.

$\alpha_i$  is a fixed effect due to modality  $i$ ;  $\sum \alpha_i = 0$

$s_l$  is a random effect due to site  $l$ ;  $s_l \sim N(0, \sigma^2_s)$ , and the  $s_l$  are independent.

$r_{f(l)}$  is a random effect due to reader  $f$  nested within site  $l$ ;  $r_{f(l)} \sim N(0, \sigma^2_r)$ , and the  $r_{f(l)}$  are independent

$\beta_{h(l)}$  is a random effect due to case  $h$  nested within site  $l$ ;  $\beta_{h(l)} \sim N(0, \sigma^2_\beta)$ , and the  $\beta_{h(l)}$  are independent.

$\varepsilon_{ilfh}$  is the random error;  $\varepsilon_{ilfh} \sim N(0, \sigma^2_\varepsilon)$ .

The random components are independent from each other.

Using model (1), the difference in major discordance rate ( $\pi_{WSI} - \pi_{Glass}$ ) will be estimated and corresponding two-sided 95% confidence interval (CI) will be derived. If the upper bound of the 95% CI is less than the non-inferiority margin of 4%, then WSI will be considered non-inferior to Glass.

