##### **11.2.1 Accuracy by Site, Reader, Organ, and Case Subtype/Procedure**

###### **11.2.1.1 Accuracy by Site**

To describe the accuracy of WSI relative to Glass by site, the MMRM logistic model (1) with the omission of the site variable will be used. For each of the four sites, the estimated major discordance rates for the two modalities, their difference ( $\pi_{WSI} - \pi_{Glass}$ ), and their corresponding two-sided 95% CIs will be presented in

tabular format. In addition, cross tabulation of the observed, unmodeled major discordance rates for the two modalities will be presented as well.

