### 11.3 Analysis Software

All analyses will be performed using SAS Software version 9.4.

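### In the by-organ analysis, non-convergence is the only reason to drop model (1), but a fit with zero major discordances in one modality can be flagged as converged and give an uninterpretable 95% CI

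*SAP*

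**What the plan says.** SAP 11.2.1.3 applies model (1) separately to each organ and adds: "The analyses will be the same as those for accuracy by site". SAP 11.2.1.1 defines that output: "For each of the four sites, the estimated major discordance rates for the two modalities, their difference", and "their corresponding two-sided 95% CIs will be presented in" a table. Each organ row is therefore meant to carry two modeled rates, a modeled difference and their intervals.

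Model (1) is a mixed logistic regression: "Modality (Glass or WSI), will be included in the model as fixed effect; and, site, reader, and case will be included as random effects".

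The SAP recognises that "sample sizes are small for some organs, e.g., hernial/peritoneal, gallbladder, appendix, etc". Its only provision for this is: "Should convergence not be reachable for model (1), cross tabulation of the observed, unmodeled major discordance rates for the two modalities will be presented". It sets no minimum event count and has no rule for a zero cell.

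The next sentence of 11.2.1.3 begins "In all cases, the observed, unmodeled major discordance rates for the two modalities" and promises these, with the WSI minus Glass difference, for every organ. It mentions no interval for them, although Protocol 9.4.3 plans 95% CIs for rates and differences within each organ.

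On computing, SAP 11.3 says only: "All analyses will be performed using SAS Software version 9.4". No estimation method or convergence criterion is given. For subtype/procedure combinations, SAP 11.2.1.4 drops the model in advance because the samples are small.

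**The concern.** If one modality has no major discordances in an organ, the maximum-likelihood estimate of the modality effect is infinite. The likelihood rises towards a plateau and flattens. A stopping rule based on the gradient is then met at some large, arbitrary value, and the software can report success. The SAP's exit does not fire, and the row keeps modeled estimates and intervals that describe where the optimizer stopped rather than the data.

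The by-organ difference is a listed secondary endpoint (SAP 3.2.2). A row of 10 cases with no WSI events could show a WSI rate of zero with an upper limit of a few thousandths of a percent, or an interval spanning everything. Neither tells the reader what 40 reads of 10 cases can exclude.

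**Working it through.** **Inputs from the documents.** SAP Table 1 has 21 organ rows summing to 2000 cases. SAP section 4 has four readers reading every case in both modalities. The check 2000 × 4 = 8000 reads per modality reproduces the planned total. The rows with 20 or fewer cases are hernial/peritoneal, gallbladder and appendix (10 each), miscellaneous (15) and soft tissue tumors (20). They supply 40, 60 and 80 reads per modality.

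**Assumed inputs.** The documents give no expected major discordance rate, only a 7% ceiling for WSI (SAP 11.1.2, Supportive Analyses). I take equal true rates of 3, 5 and 7% in both modalities and a normal case effect with SD 2 on the logit scale. SD 0 serves as a sensitivity check.

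**Chance of zero events in exactly one modality.** Let q(u) be the chance that a read of a case with effect u is not a major discordance. Let a = E[q(u)^4] (no event in a case's four reads in one modality) and b = E[q(u)^8] (none in its eight reads over both). For an organ of n cases:

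P(exactly one modality at zero) = 2(a^n − b^n)

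At 5%, a = 0.8584 and b = 0.7830, so for n = 10 this is 2(0.217 − 0.087) = 0.26.

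| True rate | 10 cases | 15 cases | 20 cases | 50 cases |
|---|---|---|---|---|
| 3% | 35.8% | 29.0% | 21.1% | 1.6% |
| 5% | 26.1% | 15.1% | 7.9% | 0.1% |
| 7% | 17.3% | 7.3% | 2.8% | <0.1% |

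For at least one of the five small rows, treated as independent:

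- 3%: 1 − 0.642³ × 0.710 × 0.789 = 85%
- 5%: 1 − 0.739³ × 0.849 × 0.921 = 68%
- 7%: 1 − 0.827³ × 0.927 × 0.972 = 49%

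With SD 0 the corresponding figures are 88, 59 and 30%. Leaving out the miscellaneous row, which is a filler category, the SD 2 figures become 79, 63 and 45% (at 5%: 1 − 0.739³ × 0.921).

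**Is such a fit flagged as converged?** SAS was not available, so these are simulated data sets fitted with other software.

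| Fit | Flagged converged |
|---|---|
| Quadrature, random case effect only; 10, 15 and 20 cases | 655 of 669 |
| Laplace, site, reader and case effects; 10 cases | 60 of 60 |
| Same; 20 cases | 57 of 60 |
| Pseudo-likelihood, stop on relative change in fixed effects, 20 outer iterations; 10 cases | 0 of 12 |

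In all 120 Laplace fits the modality effect was below −10 logits. Under pseudo-likelihood the effect moved by about one logit per outer iteration and did not settle, so the SAP's fallback would have been triggered.

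**What the row would show.**

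- Glass 3/40, WSI 0/40 (quadrature): converged, log-odds −14.8 with SE 768. The WSI rate is 0.000%, with an upper limit of 0.007% by the delta method or an interval of 0 to 100% from the logit scale.
- Glass 4/40, WSI 0/40 (Laplace): converged, effect −27.5 with SE about 2.7 × 10⁵. The delta-method SE of the WSI rate is about 2 × 10⁻⁸, against 0.042 for Glass. The difference is −6.85% ± 1.96 × 4.2%, that is −15.1% to +1.4%. All of that width comes from Glass.

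**What the data can support.** The exact 97.5% upper limit at zero events is 1 − 0.025^(1/m). It is 8.8% for m = 40 (reads independent) and 30.8% for m = 10 (a case's four reads fully correlated). These bracket the answer.

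**The case against.** A reader might infer that model (1) will normally converge in these rows, so that the small-organ table is bound to carry meaningless intervals. The documents do not support that. The outcome depends on an estimation method and stopping rule that the SAP does not state, and model (1) is written with a normal residual term, so a pure likelihood fit cannot be presumed. Under pseudo-likelihood with a parameter-change stop, the exit works as intended. In two of the Laplace examples (2/40 against 0/40 over four sites, and 3/80 against 0/80) no usable standard error came out despite the convergence flag, which an analyst would probably notice.

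A reader might also count rows with zero events in at least one modality, which gives 56/35/21% for a 10-case organ. That adds rows with zero in both modalities, which are not the situation worked through here.

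Nor should the near-zero width be attributed to the difference, which is the endpoint. In the 4/40 against 0/40 example the CI for the difference is wide, though it leaves out the WSI uncertainty. The 4-point margin and the 7% limit apply to the overall comparison, not to single organs, and SAP 11.2 makes the secondary analyses descriptive with no hypothesis testing. The observed zero would also stand in the table for every organ.

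All of this stands, and it limits the point. It does not remove it: the observed rates have no stated interval, so nothing in the table would correct the modeled one.

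**Conclusion.** Convergence alone is an inadequate trigger. With zero events in one modality, a likelihood-based fit would usually pass the SAP's check and the modeled CI would not be interpretable. Whether that happens turns on a software setting the SAP leaves open.

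The exposure is confined to the small rows: about 17 to 36% for each 10-case organ and 49 to 85% for at least one of the five rows. It is under about 2% from 50 cases up. These figures rest on equal true rates of 3 to 7%, a case SD of 2 logits and independent rows; with no case heterogeneity the five-row range is 30 to 88%. A descriptive secondary table is affected. The primary conclusion is not.

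**What to change.** In SAP 11.2.1.3, replace the convergence trigger with three conditions. Model (1) estimates are reported for an organ only if the fit converges, each modality has at least one major discordance, and the modality effect and its standard error are finite and not extreme, with numerical limits set in advance.

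Otherwise, report the observed rates and the observed WSI minus Glass difference with 95% intervals that remain valid at zero counts and treat the case as the cluster. One option is a score or exact interval for each rate with a design-effect-adjusted sample size, and a score-based interval for the paired difference adjusted for clustering by case. A row with zero events cannot supply its own within-case correlation, so the SAP should say where that value comes from, for example all organs pooled.

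State the SAS estimation method and convergence criterion alongside model (1).

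The cost is a few sentences and a short program; a few small organs lose a modeled estimate. A higher threshold, such as five events per modality, would cost more. Under the SD 2 assumption it would remove the model for a 50-case organ about 50% of the time at a 3% rate and about 11% at 5%, and Table 1 has four such organs.

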#### 11.2.1.4 Accuracy by Case Sub-type/procedure

As shown in Table 1, sample sizes are generally small for case sub-type/procedure combinations and non-convergence is likely for model (1). Therefore, cross tabulation of the observed, unmodeled major discordance rates for the two modalities will be presented for each case sub-type/procedure combination.

### 11.3 Analysis Software

All analyses will be performed using SAS Software version 9.4.

## 12. REVISION HISTORY

Version	Date	Description
1.0	18 JUN 2019	Original release
2.0	01 AUG 2021	Updated to reflect revised analyses based on communication with FDA through Q-Sub process

---

